7.4 Reporting Procedures

The PI will use standardized NIA forms to report all adverse effects (AEs) and serious adverse effects (SAEs) (except death) in writing to the NIA Program Officer (PO), Safety Officer (SO) and Rush University IRB on a **quarterly** basis.

Any Unanticipated SAEs not listed in the Data Safety Monitoring Plan related to the intervention will be reported by the PI on an expedited basis within **48 hours** from determination of occurrence to the NIA PO, SO, and IRB, following-up with a written corrective plan with measures to prevent reoccurrence.

The PI will report any participant death whether or not related to study participation and regardless of intervention condition to NIA PO, SO, and IRB on an expedited basis within **24 hours** from determination of occurrence.

Unanticipated problems including other incidents, outcomes, or experiences that are not SAEs (e.g. data breach, confidentiality threat) will be reported by the PI using standardized forms to NIA PO, SO, and IRB within **48 hours**, including a corrective plan and measures to prevent reoccurrence. .

7.5 Follow-up for Adverse Events

Participants experiencing AEs will be referred for outpatient or inpatient treatment (depending on severity). Follow-up will span the 24-week duration of the study participation.

7.6 Safety Monitoring

The Principal Investigator (PI) will be responsible for ensuring participant and data safety on a daily basis. As a Stage I, single site, and minimal risk study, we will establish an internal committee to assist with data safety monitoring (DSM). In addition, an NIA-approved Safety Officer (SO) will oversee the DSM, and will review data and adverse events twice per year and more frequently if necessary. The SO will act in an advisory capacity to the NIA Director and PO to monitor participant safety, evaluate the progress of the study, and to review procedures for maintaining the confidentiality of data, the quality of data collection, management, and analyses.

8 INTERVENTION DISCONTINUATION

CGMI-V is a Stage I, single site, minimal risk behavioral intervention study. There is no anticipated intervention discontinuation for this study. Study participants may withdraw voluntarily from participation in the study at any time and for any reason. We will continue to follow these participants, with their permission, at the 8 and 24 week assessment points. Participants in the CGMI-V condition who discontinue early will not be replaced, as this is a group-based intervention where “the dose” consists of eight consecutive weekly group sessions.

9 STATISTICAL CONSIDERATIONS

9.1 General Design Issues

CGMI-V is a Stage I longitudinal randomized clinical trial. ADRD caregivers whose family members are in long-term care facilities (LTCFs) will be recruited, screened for inclusion criteria, and randomly assigned to either CGMI-V or a Minimal Treatment (MT) control condition. Caregivers in the CGMI-V condition will participate in eight weekly professionally led, real-time, live-streaming video online group sessions. Those caregivers in the MT control condition will receive written information materials about late-stage ADRD at baseline. For both conditions, data will be collected at baseline (pre-intervention), 8 weeks (immediately post-intervention) for intervention effects, and 24 weeks post baseline for maintenance effects. The design for this study was chosen to avoid the type of group clustering or contamination that would be engendered by the use of a randomized cluster design. The study hypotheses are outlined below:

Primary Hypothesis

Hypothesis 1: We hypothesize that caregivers in the CGMI-V condition compared to those in the MT control condition, will report decreased chronic grief levels.

Secondary Hypotheses

Hypothesis 2: We hypothesize that caregivers in the CGMI-V condition compared to those in the MT control group will report (2.1) decreased symptoms of depression and anxiety and (2.2) increased positive mental states.

Hypothesis 3.1 and 3.2: We hypothesize that caregivers in the CGMI-V condition compared to those in the MT control condition will report (3.1) increased satisfaction with care provided in the facility and (3.2) decreased conflict with staff.

Mechanism of Intervention Hypothesis

Hypothesis 4: We hypothesize that CGMI-V works by changing the exacerbators of chronic grief: lack of knowledge, sense of loss, guilt, and role captivity.

Primary Outcome Measures

Caregiver Chronic Grief will be measured with the 50-item Marwit-Meuser Caregiver Grief Inventory (MM-CGI).⁶ This inventory has three subscales: (1) *Personal Sacrifice Burden*: 18 items measuring individual losses experienced as a result of caregiving, (2) *Heartfelt Sadness and Longing*: 15 items measuring interpersonal emotional reactions in response to caregiving, and (3) *Worry and Felt Isolation*: 17 items measuring feelings of losing connections with, and support from, others. Items are rated on a 5-point scale (1 = *strongly disagree* to 5 = *strongly agree*), with a possible range of 50 to 250 points. Grief scores may be calculated by subscale and then added to formulate a total grief score. Total grief scores above 175 indicate high levels of caregiver grief, requiring formal intervention and support. Cronbach's alpha subscale scores range from .90 to .96, indicating high internal consistency reliability for each subscale and for their combined total grief score. Test-retest Cronbach's alpha scores range from .71 to .75, indicating stability of the measure over time in all three subscales.¹⁵

Secondary Outcomes Measures

Depressive symptoms will be measured with the 20-item version of The Center for Epidemiological Studies Depression Scale (CES-D).⁴⁰ Responses are based on a four-point frequency rating (0 = *rarely or none of the time* to 3 = *all of the time*), with a possible range of 0 to 60. A score above 16 indicates existence of depressive symptoms. Internal consistency reliability range $r = .85$ to $.90$, and test-retest reliability $r = .45$ to $.70$.⁴⁰

Anxiety symptoms will be measured with the 20-item State-Anxiety subscale of the State-Trait Anxiety Inventory (STAI).⁴¹ Responses are based on a scale of 1 to 4 (1 = *almost never* to 4 = *almost always*), with a possible range of 20-80, where higher scores indicate greater anxiety. Alpha coefficients for older adults range .90-.92, indicating high internal consistency reliability.⁴¹

Positive States of Mind will be measured with the Positive States of Mind Scale (PSOMS)⁴² to assess the extent to which caregivers were able to achieve six positive states of mind in the previous seven days. Other studies²¹ found that caregivers who scored high on the PSOMS also scored lower on the grief scale. The scale comprises six items that capture: (1) focused attention, (2) productivity, (3) responsible caregiving, (4) restful repose, (5) sensuous nonsexual pleasure, and (6) sharing. The responses range from 0 = *unable to achieve* to 3 = *easy to achieve*. Cronbach's alpha coefficient was .77, indicating high internal consistency reliability.

Conflict with facility staff will be measured with a subscale of the Family Perception of Caregiving Role (FPCR). The 61-item FPCR^{3,30} contains four subscales to measure dimensions of role stress: (1) loss of relationship aspects with care recipient, (2) guilt from perceived failure in caregiving, (3) captivity resulting from obligations of caregiving, and (4) conflict with facility staff related to caregiving. Responses are rated on a 7-point Likert scale (1 = *strongly disagree* to 7 = *strongly agree*), with a possible range of 61 to 427. Items are summed to form subscale scores and a total FPCR score. Cronbach's alpha coefficients ranging from .70 to .84 indicate high internal consistency reliability for each subscale and for the total FPCR score. Test-retest reliability was .79 for FPCR total score.^{3,30} We will score the 10-item Conflict with Facility Staff subscale; its Cronbach's alpha coefficient is .84.

Satisfaction with care will be measured with the Family Perceptions of Care Tool (FPCT).^{3,30} The 51-item FPCT contains four subscales that reflect caregivers' perceived satisfaction with: (1) physical care provided to their family member in the facility, (2) activities for facility residents, (3) unit management, and (4) staff consideration for resident and family member. Responses are rated on a 7-point Likert scale (1 = *strongly disagree* to 7 = *strongly agree*), with a possible range of 51 to 357. Items are summed to form subscale scores and a total FPCT score. Cronbach's alpha coefficients ranging from .85 to .97 indicate high internal consistency reliability for each subscale and for the total FPCT score. We will use all 51 items to assess caregiver satisfaction with care received in the LTCF.^{3,30}

Exacerbators of Chronic Grief

We will measure four exacerbators of ADRD caregiver chronic grief: (1) caregiver lack of knowledge about dementia, (2) caregiver perception of loss, (3) guilt, and (4) role captivity.

Knowledge of dementia/AD will be measured with the 22-item Family Knowledge of Alzheimer's Test (FKAT).³⁰ This instrument captures what a family caregiver knows about the disease process, how the care recipient is behaving, and how the LTCF is caring for him or her. Responses are based on a true/false scale, with a maximum score of 22 correct answers. Test-retest reliability was .82 ($p < .05$), KR 21 ($n = 50$) = .61.

Loss will be measured with the 7-item Loss subscale of the FPCR^{3,30} (full description above). Cronbach's alpha for this subscale was 0.73.

Guilt will be measured with the 5-item Guilt subscale of the FPCR^{3,30} (full description above). Cronbach's alpha for this subscale was 0.70.

Role captivity will be measured with the 7-item Captivity subscale of the FPCR^{3,30} (full description above). Cronbach's alpha for this subscale was 0.81.

Background Measures

Caregiver and care recipient socio-demographics. To describe caregiver and care recipient baseline background data, we will collect standardized information. These survey questions are drawn from the initial population survey used by the East Boston site for the Established Populations for Epidemiologic Studies of the Elderly project (EPES).⁴³ Situational characteristics. Three direct questions will be asked at baseline to assess: (1) number of years since the care recipient was diagnosed with ADRD, (2) time since placement in the LTCF, and (3) visiting pattern in the LTCF (times per week and number of hours per visit).

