These findings suggest that the 5 weeks may have been too short for caregivers to process their grief. A longer grief intervention (5 months) was used by other investigators.²⁴ That intervention included community-based ADRD spouse caregivers who received individualized sessions delivered weekly over 5 months with follow-up at 8 months post baseline. At five months, improvements were found in grief, symptoms of depression, and anxiety for all participants. At the eight-month post-baseline follow-up, the positive outcomes were sustained for all except those caregivers whose spouses had been placed in long-term care or had died. These findings suggest that ADRD caregivers needed to continue receiving a grief intervention even after they placed their family member in long-term care to maintain improvements in grief and symptoms of depression and anxiety.²⁴ Therefore, we created an intervention that targets ADRD caregiver's chronic grief after LTC placement based on a grief-centered paradigm that expands the existing Stress Process Model.

We designed the **Chronic Grief Management Intervention (CGMI)** for ADRD Caregivers (PI: [name]; Co-Is [name], & [name]). Funding: NINR-R21NR010577, 2008-2011.^{25,26} as a 12-week group intervention to improve caregivers' (1) knowledge of late-stage ADRD; (2) communication, conflict resolution, and chronic grief management skills; and (3) grief and mental health outcomes. We pilot-tested the effects of CGMI in a pre-test/multiple post-test design with random assignment of 16 long-term care facilities to either the 12-week CGMI or an attention control condition. Data were collected at baseline, 3 months (immediately post-intervention) and 6 months (post-baseline). The content was structured into three major components: (1) knowledge about late-stage ADRD, (2) communication and conflict resolution skills, and (3) chronic-grief-management skills. Those in the attention control condition received two brief minimal-support phone calls at weeks 6 and 18.

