Study population and location: We will recruit a sample of 144 ADRD caregivers who have a family member residing in dementia care or memory care units in long-term care facilities located in the Chicago metropolitan area. We have well-established collaborating relationships with 35 long-term care facilities that will give us access to a diverse pool of approximately 1,000 ADRD family caregivers. Caregivers will be randomly assigned to either the CGMI-V condition (n=72) or the MT control condition (n=72). Caregivers will receive the CGMI-V intervention at home or another location of their choosing, using iPads with an online platform (WebEx). Caregivers in the MT condition will receive written

information about late stage ADRD at baseline. Each individual caregiver is expected to be in the study for a total of 24 weeks from enrollment to follow-up.

Study implementation: The study will be implemented in six waves. Beginning in Month 5 of the study, we will start recruiting and enrolling 24 caregivers for Wave 1, who will be randomly assigned to either the CGMI-V condition ($n = 12$; 6/group) or MT control condition ($n = 12$). After these 24 caregivers have been enrolled, the study team will start recruiting and enrolling an additional 24 caregivers for Wave 2. There will be a total of six waves. Each wave will have 8 weeks to recruit, screen, enroll, randomize to condition, and complete baseline data collection, followed by 8 weeks to implement the intervention condition, and data collection immediately post-intervention and 24 weeks from baseline follow-up. Once enrollment is completed for a wave, recruitment will start for the following wave. This pattern will be the same for all six waves. This will result in 144 caregivers being enrolled, 72 for the CGMI-V condition, and 72 for the MT control condition. Figure 1 illustrates the progression of the study waves through the study timeline.

Figure 1. Ordering of Administering Treatment Conditions

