Intervention: For the CGMI-V intervention condition, study materials (participant manual, technology instructions) will be sent to participants electronically. We will mail hard copies of the manual and technology instructions to those caregivers who prefer to have them printed out. The iPad tablet and the earbuds with microphone will be mailed to participants prior to the first session. As needed, caregivers will receive an individualized over-the-phone orientation (20-30 minutes) in the operation of the equipment from the technology assistant. Each session will start with a brief technology check-up and review of ground rules including maintaining confidentiality.

Each CGMI-V group session will be conducted by one interventionist who has therapeutic group leading experience. For treatment fidelity purposes, the study interventionists will be trained in the delivery of the group intervention and the iPad and online technology. Each group will have not more than six participants. The intervention consists of approximately 60-minute sessions delivered weekly for eight consecutive weeks and will follow the standardized CGMI-V intervention manual (Appendix A).

The purpose of the CGMI-V is to improve ADRD caregivers' (1) knowledge about late-stage ADRD; (2) communication and conflict resolution skills, and (3) skills managing their loss and chronic grief. Sessions 1-2 address caregiver knowledge about late-stage ADRD, and the resources available to dementia families in the LTCF and the community at large.^{3,28} Sessions 3-4 address caregiver skill in communication and conflict resolution and hands-on care in the context of LTCF.^{3,15-17,28-30} Sessions 5-8 address caregiver loss and grief management skills using discussion guides tailored to specific grief management topics.³¹⁻³⁷ The participant manual outlines each session's content and includes questions to facilitate discussion. Additional materials are provided for knowledge and skill topics. These are fact sheets about late-stage ADRD that are published by the Alzheimer's Association, a guide with resources for ADRD family caregivers published by the Family Caregiver Alliance, and a chapter on hospice services (Appendix A).

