Control condition. Caregivers in the control condition will receive Minimal Treatment (MT) consisting of written information about late-stage ADRD (Alzheimer's Association) at baseline. The Project Director will mail caregivers in the MT control condition all written information materials.

4 **SELECTION AND ENROLLMENT OF PARTICIPANTS**

We will recruit a sample of 144 ADRD caregivers who have a family member residing in dementia care or memory care units in long-term care facilities located in the Chicago metropolitan area. We have well-established collaborating relationships with 35 long-term care facilities that will give us access to a diverse pool of approximately 1,000 ADRD family caregivers.

4.1 **Inclusion Criteria**

Participants must meet all inclusion criteria listed below in order to participate in this study.

- 21 years of age or older
- Identified as family member, fictive kin (self-identified family member) or partner of care recipient at any time post permanent placement of care in LTCF
- Care recipient has a documented ADRD diagnosis and resides in any type of unit in a long-term care facility
- Possessing self-reported basic computer literacy and in-home internet access
- Able to speak, read, and write English
- Not currently attending another ADRD caregiver grief management group

- Experiencing high to moderate levels of grief per screening with the Marwit-Meuser Caregiver Grief Inventory-Short Form (scores 25 or above), and/or experiencing high levels of depressive symptoms per screening with PHQ9 (scores 10 or above)
- Caregivers whose care recipients die during the course of the intervention will remain in the study

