9.2.1 Treatment Assignment Procedures

The study is a Stage I longitudinal randomized clinical trial. ADRD caregivers whose family members are in LCTFs will be recruited, screened for inclusion criteria, and randomly assigned to either CGMI-V or a Minimal Treatment (MT) control condition. Randomization will be stratified in six Waves of 24 participants each, to insure that there are exactly 12 participants in each condition. In Wave 1, we will randomly assign the first 24 enrolled participants to either the CGMI-V condition ($n = 12$; 6/group) or MT control condition ($n = 12$). The same process will continue for the next five Waves. Recruiters and data collectors will be blinded as to the random assignment of each participant. Once caregivers sign the consent to enroll in the study, the Project Director will use randomization software to assign each enrolled participant to CGMI-V or the MT condition. The Project Director will then inform the participants directly of their assignments and ask them to maintain confidentiality about their assignment at data collection points.

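### Section 9.1 credits the design with avoiding contamination, but caregivers are randomised individually within shared facilities and two relatives of one resident may both enrol; the likely bias is modest and towards zero.

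*Combined protocol and SAP*

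**What the plan says.** Section 9.1 gives the reason for the design: it was "chosen to avoid the type of group clustering or contamination that would be engendered by the use of a randomized cluster design". Section 9.2.1 makes the caregiver the unit of allocation: "the Project Director will use randomization software to assign each enrolled participant to CGMI-V or the MT condition". The only stratum is the wave: "Randomization will be stratified in six Waves of 24 participants each, to insure that there are exactly 12 participants in each condition". Neither facility nor resident enters the allocation.

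Section 3 describes "well-established collaborating relationships with 35 long-term care facilities" as the recruitment base for both arms. The relationship criterion in 4.1, repeated in the 6.2.1 screen, is "Identified as family member, fictive kin (self-identified family member) or partner of care recipient". Neither these lists nor the exclusions in 4.2 limit entry to one caregiver per resident.

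For the intervention arm, Section 3 says that "study materials (participant manual, technology instructions) will be sent to participants electronically", with printed copies for those who prefer them. The team's earlier 12-week pilot (Section 2.2) used "random assignment of 16 long-term care facilities to either the 12-week CGMI or an attention control condition".

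Three provisions touch on confidentiality. Under 9.2.1 the Project Director tells participants their assignment and will "ask them to maintain confidentiality about their assignment at data collection points". In Section 3, sessions open with ground rules that include confidentiality. In 11.3, iPads and session links are password protected. Section 9.5 analyses by intention to treat and describes the multilevel model as handling autocorrelation over the three time points.

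**The concern.** Randomising facilities keeps the arms apart. Randomising individuals who share a facility puts both arms among the same families, staff and events. On contamination, then, the rationale in 9.1 credits this design with an advantage that belongs to the alternative it rejects.

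The closest route is within a family. Two siblings, or a spouse and a child, could both qualify and be split between arms, with the manual and the discussions at hand. None of the three confidentiality provisions is aimed at this. The first protects assessor blinding; the other two protect group privacy and access. The documents describe no measure of MT exposure to CGMI-V content and no adjustment for it.

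Two relatives would also rate the same facility's care and staff and share any death or discharge of the resident. They would be correlated observations even if they exchanged nothing.

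The trial's product is an effect size for judging whether a larger trial is justified (9.5), so a bias in one direction deserves attention even when it is small.

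**Working it through.** **The plan's own figures (9.2), as the yardstick.** SD 35.78, 64 evaluable per arm, 10% attrition.
- 35.78/√64 = 4.47; 1.96 × 4.47 = 8.77 units; 8.77/35.78 = 0.245, the plan's 0.25 SD.
- 64/(1 − 0.10) = 71.1, rounded up to 72 per arm. The stated sizing reproduces.
- The 4.47 is the standard error of one arm's mean. For the difference between arms it is 35.78 × √(2/64) = 6.33, with half-width 1.96 × 6.33 = 12.40 units or 0.35 SD. Both yardsticks are used below.

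**Mixing within facilities.** 144/35 = 4.1 participants per facility if spread evenly (an assumption). With four participants and approximately independent 1:1 allocation, the facility holds both arms with probability 1 − 2 × 0.5⁴ = 0.875. This shows that contact is possible, not how much content passes.

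**Splitting of relatives.** In a wave of 24 allocated 12:12, two given people fall in opposite arms with probability 12/23 = 0.52. In different waves it is 0.50.

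**Dilution by the family route.** The documents give no rate of shared residents. Assume that 5-15% of the 144 share a resident with one other participant, with both in the same wave.

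| Step | 5% | 15% |
|---|---|---|
| People sharing a resident | 7.2 | 21.6 |
| Pairs (rounded) | 4 | 11 |
| Split pairs = exposed MT caregivers (× 12/23) | 2.1 | 5.7 |
| Share of 72 MT caregivers, c | 2.9% | 8.0% |

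If an exposed MT caregiver gets the whole CGMI-V effect, the observed effect is d(1 − c), a loss of 3-8%. Full transfer makes this the ceiling for this route at the assumed rate.

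For scale, take the largest pilot effect in 2.2, 0.49. It belongs to one subscale, not to the MM-CGI total. The loss is 0.49 × 0.029 = 0.014 to 0.49 × 0.080 = 0.039 SD, the latter being 0.039 × 35.78 = 1.4 units. That is at most 0.039/0.25 = 16% of the plan's stated half-width, or 0.039/0.35 = 11% of the between-arm half-width.

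**Non-independence.** Let ρ be the within-pair correlation. For a simple difference in means with 72 per arm, each pair in the same arm raises the variance and each split pair lowers it. The relative change is ρ × (same-arm pairs − split pairs)/72. With 11 pairs, the expected change is ρ × 11 × (11/23 − 12/23)/72 = −0.007ρ. If all 11 happened to fall together it would be 11ρ/72 = 0.15ρ. The expected effect on precision is therefore close to nil, although the model as described would not represent the pairing.

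**The case against.** The strongest reply is that the harm is small and rests on silence. No passage says that relatives will enrol together, and neither pilot description reports it. Section 3 counts about 1,000 caregivers and Section 12 the caregivers of more than 1,000 residents, which hints at planning on about one per resident without requiring it. Full transfer is also implausible. Sessions are live, led by a professional, taken at home or another chosen place and reached through protected links. The grief component in sessions 5 to 8 depends on group processing, so holding the file is not receiving the treatment. MT caregivers already get Alzheimer's Association material on late-stage disease, so part of the knowledge content is common by design. Relatives in distant waves may overlap little. All of this stands, and it puts realistic dilution below the ceiling.

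It can also be said that 9.1 means only facility effects entangled with treatment. That reading rescues the clustering half of the sentence. It does not rescue the word contamination, which facility randomisation would limit.

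The manuals and consent form are listed by title only, so an instruction not to share content may exist there. That would reduce the exposure but would not restrict entry or remove the pairing.

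A reader might infer that the trial will reach a wrong effect size or a wrong decision against a larger trial. The documents do not support that: the shift is small beside the precision, and 9.5 sets no numerical threshold for it to cross. Nor does the point imply that facilities should be randomised; individual randomisation can stay.

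**Conclusion.** The contamination rationale in 9.1 is wrong as worded, and the entry rules leave open the closest route of exposure. About half of any enrolled pairs of relatives would be split between arms, and all such pairs would be correlated in a model with no resident-level term. The expected direction is a modest bias towards zero: at most about 3-8% of the effect by the family route if 5-15% of participants share a resident and transfer is complete, and probably less. Both conditions are assumptions without a source in the documents. Exposure through wider contact at the facility is possible but cannot be sized from them. No wrong conclusion is demonstrated. The case for acting is that the correction is cheap and keeps a mistaken rationale out of the design of the next trial.

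**What to change.** Add to 4.1 and to the 6.2.1 screen: *One caregiver per care recipient; the first to consent is enrolled.* Reword 9.1 to say that individual randomisation avoids facility-level clustering of assignment but does not prevent contamination between arms within a facility.

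The cost is one screening question and one sentence. The downside is that a few otherwise eligible second relatives are turned away, from a pool of about 1,000 for 144 places. The rule removes the split-relative route and the paired observations. It leaves contact between unrelated caregivers in the same facility as it is, and the reworded 9.1 should not suggest otherwise.
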